## 11.2 Sample Size Determination

Study enrollment has been closed since 15 Oct 2008 and no new study participants will be enrolled.

The sample size for the postapproval study originally was determined in the following manner:

*It is assumed that it is required to have 80% power to be able to detect as statistically significant a relative risk of 2.0 for adverse events that occur, without implants, with a frequency of 2.85 per 100,000. This figure is based on the incidence of scleroderma as reported by Mayes et al. (2003). It is assumed this would be based on a one-sided test conducted at the  $\alpha = 0.05$  level of significance. Based on these specifications, it was determined that approximately 338,000 person-years would be required.*

*Patients are to be followed for 10 years. For purposes of sample size calculation, assuming a follow-up rate of 65% at 10 years and a linear loss to follow-up, there would be an average of 8.075 person-years per participant. Thus, in order to obtain the 338,000 person-years, a total of 41,900 MemoryGel participants would be required.*

*The concurrent control sample size was selected in order to be able to detect a relative risk of 2.0 for MemoryGel participants as compared to control participants, for rheumatologic and neurologic signs and symptoms with a prevalence of approximately 2% among MemoryGel participants. It is assumed this would be based on a one-sided test conducted at the 0.05 level of significance with a power of 80%. Similar combined rheumatologic categories of signs and symptoms from Mentor's existing Core Study of these silicone gel implants all have estimated prevalence of at least 2% after year 2. These data will be analyzed by first computing, for each participant, the proportion of time points in which the participant reports the sign or symptom as being prevalent and then calculating the mean of these participant-level proportions across participants within each group. For purposes of sample size calculation, it is assumed that these means will be compared using a simple test based on the normal approximation.*

*Given an expected 65% follow-up rate at 10 years, it is assumed participants will have reports, on average, at 8 time points. The correlation between different reporting time points for an individual participant is taken into account. From Mentor's existing Core Study of silicone gel-filled breast implants, for the three combined categories of signs and symptoms correlations between time points that are 1 year apart range from 0.47 to 0.59, and correlations between time points that are 2 years apart range from 0.35 to 0.41. As expected, the correlations decrease with distance between time points. On average, considering all pairs of time points and ignoring loss to follow-up, time points will be 3.7 years apart. (For example, years 1 and 3 are 2 years apart and years 1 and 10 are 9 years apart.) Thus, it is assumed that the correlation, on average, would not be higher than 0.30. Based on the above, it was determined that a sample size of 1,000 concurrent controls would be more than sufficient.*

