## 1.0 INTRODUCTION

On 17 Nov 2006, the U.S. Food and Drug Administration (FDA) approved Mentor's MemoryGel® silicone gel-filled breast implants for use in women who are undergoing primary or revisional breast augmentation and primary or revisional breast reconstruction surgery. The approval was conditional on Mentor conducting a 10-year study designed to collect long-term experience in U.S. women with MemoryGel implants. The MemoryGel Postapproval Study (MemoryGel PAS) is intended to satisfy one element of FDA's postapproval requirements.

As a condition to gaining access to MemoryGel products, physicians were required to sign up for the MemoryGel Gel-Filled Breast implants Post Approval study, and were asked to actively encourage 41,900 women to participate in the 10-year study. In addition, the study included 1,000 women who were undergoing breast implantation with saline breast implants to serve as concurrent controls for assessing rheumatologic and neurologic signs and symptoms.

Approximately 1,700 centers participated in the study and enrollment included 41,451 MemoryGel participants and 1039 saline participants. Study enrollment has been closed since 15 Oct 2008. As of the last annual study report (dated Nov 2013), the follow-up rates through six years were 21.8% for MemoryGel participants and 15.0% for saline participants.

Due in part to the low follow-up rate, which may limit interpretation of the data, FDA in collaboration with the American Society of Plastic Surgeons (ASPS), breast implant manufacturers, and patient representatives have been investigating innovative approaches to collect long-term data on silicone gel breast implants. As part of these efforts, recently, FDA has agreed to changes in the postapproval commitments for the MemoryGel silicone gel-filled breast implants that include changes to MemoryGel PAS. These changes are described in this amended protocol.

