This amended protocol limits the scope of data collection under the original protocol to the collection of only secondary procedure/reoperation data. There are no longer requirements for scheduled office visits or annual participant questionnaires, which included the collection of data on conditions and diseases such as connective tissue disease, rheumatological signs and symptoms, and neurological disease. The limited data collected under this protocol amendment are similar in scope to the data collection planned for the National Breast Implant Registry, and therefore, this amended protocol will serve as a pilot for the future registry efforts.

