#### Complications/Reoperations

The cumulative incidence of key local complications (explantation, and reoperation) for women with MemoryGel implants will be estimated based on physician evaluations for the MemoryGel participants using Kaplan-Meier methodology to estimate the time to the first occurrence of the complication or reoperation. Ninety-five percent confidence intervals will be computed. In addition, the relative frequency of reasons for reoperation will be computed.

Under the original protocol, the purpose of the inclusion of the saline participants was to serve as concurrent controls for assessing rheumatologic and neurologic signs. Rheumatological and neurological data will not be collected under this protocol amendment.

Mentor will generate the following final clinical study reports for submission to FDA:

- One final report at the end of the study phase conducted under Amendment 1, including data from beginning of the study through the end of the study phase under Amendment 1. The statistical analysis will be conducted as described in the original protocol (see below).
- One final report at the end of the study phase conducted under Amendment 2, including data from the execution of Amendment 2 to the end of the study. The statistical analysis will be conducted as described above.

The original analyses conducted to address each of the postapproval study's original objectives are identified below and correspond to issues outlined in Table 1:

*It is important to recognize that this study is observational. As a result, data from this study can be used only to establish association, not causality, and data should be evaluated within the context of the broader composite of literature relating to these issues. All of the analyses, except for the analyses of rheumatological and neurological signs and symptoms, will be based on the MemoryGel participants only.*

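### The 80% power to detect a doubling of scleroderma-rare events was not attained, and Section 11 does not say so

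*Combined protocol and SAP*

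**What the plan says.** Section 11.2 records how the MemoryGel sample size was first set: "It is assumed that it is required to have 80% power to be able to detect as statistically significant a relative risk of 2.0", for events occurring without implants "with a frequency of 2.85 per 100,000", the scleroderma incidence. The test is one-sided at 0.05, and 338,000 person-years are needed. Person-years are converted to women by "assuming a follow-up rate of 65% at 10 years and a linear loss to follow-up", giving 8.075 person-years each and 41,900 participants.

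Sections 1.0 and 4.0 report what happened. Enrolment was 41,451, and "the follow-up rates through six years were 21.8% for MemoryGel participants and 15.0% for saline participants". Section 1.0 adds that the low rate may restrict what can be concluded, but gives no figure for the effect.

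Under Amendment 2, "There are no longer requirements for scheduled office visits or annual participant questionnaires". Those questionnaires were the route for connective tissue disease data. Section 3.0 places the study in year 7.

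Section 11.1 nevertheless requires a final report on the Amendment 1 phase, for which "The statistical analysis will be conducted as described in the original protocol (see below"). The original text for connective tissue disease, cancer, neurological disease and suicide calls for a one-sided 0.05 test of relative risk against national norms, with 95% confidence intervals. Neither 11.1 nor 11.2 gives attained person-years, a revised power or a detectable relative risk.

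**The concern.** The only power statement available to a reader of the Amendment 1 report is the one in 11.2. It rests on retention that the same document shows was not achieved: linear loss to 65% at 10 years implies 79% at year 6, against a reported 21.8%. The missing person-years cannot be made up later, because disease collection stops.

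Scleroderma is the event the study was sized on. If its relative risk is not significant and is read against a nominal 80% power at 2.0, the reader could take a doubling of risk to be unlikely when the data are too sparse to say so.

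**Working it through.** **Inputs.** From 11.2: background rate 2.85 per 100,000 person-years, relative risk 2.0, one-sided 0.05, 338,000 person-years, 65% at 10 years with linear loss. From 1.0 and 4.0: N = 41,451 and 21.8% through six years. From 3.0: year 7.

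**Method.** The documents name no test. I use the exact one-sample Poisson test against a fixed rate, because it reproduces the plan's figure. With E = 2.85e-5 × person-years, reject at the smallest count c with P(X ≥ c | E) ≤ 0.05. Power is P(X ≥ c | 2E). The detectable relative risk is the R for which P(X ≥ c | R × E) = 0.80.

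**Reproducing the plan.** E = 338,000 × 2.85e-5 = 9.63 and 2E = 19.27. Reject at c = 16 (actual alpha 0.037); power is 0.802. Person-years per woman, counted at year end: sum over k = 1 to 10 of (1 − 0.035k) = 8.075. Women: 338,000 / 8.075 = 41,858, rounded to 41,900. The original arithmetic holds.

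**Study as run.** The first four rows read 21.8% as the share still followed at year 6.

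| Reading | Person-years | E | c | Power at RR 2.0 | RR detectable at 80% |
|---|---|---|---|---|---|
| Exponential loss to year 6: 41,451 × 0.782 / (−ln 0.218 / 6) | 127,679 | 3.64 | 8 | 44% | 2.8 |
| Linear loss to year 6, year-end counting: 41,451 × 3.263 | 135,255 | 3.85 | 8 | 51% | 2.65 |
| Linear loss to year 6, mid-year counting: 41,451 × 6 × (1 + 0.218)/2 | 151,462 | 4.32 | 9 | 50% | 2.6 |
| Previous row plus year 7 at 21.8%: 41,451 × 3.872 | 160,498 | 4.57 | 9 | 56% | 2.5 |
| Only 21.8% ever contribute, six years: 41,451 × 0.218 × 6 | 54,218 | 1.55 | 5 | 20% | 4.4 |
| Linear to year 6, then 21.8% held to year 10: 41,451 × 4.526 | 187,607 | 5.35 | 10 | 63% | 2.3 |
| No loss at all for 7 years: 41,451 × 7 | 290,157 | 8.27 | 14 | 77% | 2.1 |

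The 63% row is deliberately favourable, since it credits disease follow-up beyond the point where collection stops. Eight years with no loss would give 41,451 × 8 = 331,608, still short of 338,000.

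**What a null result would show.** The exact upper 95% limit for the relative risk with O events is [chi-square 0.975 quantile on 2(O + 1) df / 2] / E. At 135,255 person-years with 4 events it is 10.24 / 3.85 = 2.7. At the planned 338,000 with 10 events it is 18.39 / 9.63 = 1.9. With events close to expectation, the planned study would have excluded a doubling; the study as run would not.

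**How far it reaches.** At 135,255 person-years, power at relative risk 2.0 is about 70% for a background rate of 5 per 100,000, 90% for 10 and 99% for 20.

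**The case against.** The best defence is that 11.2 presents this calculation as history. It explains why 41,900 was chosen and does not say the study now has 80% power. It is also arithmetically right, so a reader who infers a sample-size error from the shortfall would be wrong. Amendment 2's own objectives, removal and reoperation rates and the reasons for reoperation, carry no power claim. All of that stands.

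The protocol also discloses the low follow-up and concedes that it may limit interpretation, and the 95% intervals already planned will show imprecision. Nothing in the documents says that a non-significant result will be taken to rule out a doubling. Over-reading is therefore a possibility, not something the plan commits to.

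The individual power values are also soft. Follow-up through six years is undefined, attained person-years are not reported, the test is inferred, and exact Poisson power is saw-toothed: about 81% at 320,000 person-years but 78% at 331,608. So 338,000 is not a sharp threshold, and no single row should be quoted as the answer.

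A reader might extend the shortfall to every Amendment 1 outcome or to the saline comparison. The figures do not support the first: power is adequate at background rates of about 10 per 100,000 and above. The second rests on a separate calculation (prevalence, repeated reports and their correlation) that this check does not address.

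The defence does not remove the gap. Section 11.1 keeps the original tests in force for a report to the regulator, and the general caveat in 1.0 is neither quantified nor carried into Section 11.

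**Conclusion.** The concern holds as a reporting gap. The 80% power at relative risk 2.0 was a sound design figure that the study as run does not attain for events near 3 per 100,000. Reading 21.8% as retention at year 6, person-years are about 128,000 to 160,000 (38% to 47% of plan), power is about 44% to 56%, and the detectable relative risk is about 2.5 to 2.8. The other lossy readings tabulated widen power to 20% to 63%, and no loss for seven years still gives only 77%. The direction is secure under every reading tabulated; the size depends on the undefined follow-up term, the loss pattern and the exact Poisson test. The consequence is that a non-significant scleroderma result could be over-read, not that it will be.

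**What to change.** Keep the calculation in 11.2 as the historical basis for the sample size, and add one sentence saying that its 80% power for a relative risk of 2.0 was not attained, with a pointer to the follow-up figures in 1.0 and 4.0.

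In the Amendment 1 final report, for scleroderma and similarly rare events:
- give attained person-years;
- give the relative risk detectable with 80% power at those person-years (or the power at 2.0);
- state that a non-significant relative risk does not exclude a doubling unless the upper 95% limit is below 2.0.

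This costs one calculation from data the sponsor already holds and a few sentences of text. It needs no new data and no change to enrolment. The price is a less favourable stated power.

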**12.0 INSTITUTIONAL REVIEW BOARD APPROVAL**

National or local IRB approval will be required for each site. If local IRB approval is needed then a copy of that approval should be forwarded to Mentor.

### **13.0 INFORMED CONSENT AND AUTHORIZATION OF MEDICAL RECORDS RELEASE**

Active study participants will not require re-consent as the currently approved informed consent will continue to be applicable for this protocol amendment. Less data collection is required under this protocol amendment as data collection is limited to secondary procedure/reoperation time points; however, the patient data to be collected were part of the original protocol. Therefore, this amendment does not require an informed consent addendum as there are no new risks or benefits to the patients for participating.

Refer to Section 14.0 for information on re-consenting of participants discontinued due to patient non-compliance.

A listing of participants and their status - active or discontinued (with reason for discontinuation) - will be provided to the investigative site when protocol amendment 2 is initiated.

The postapproval study was originally designed with the following informed consent requirements:

*Written informed consent must be obtained from each participant prior to the participant being enrolled into this postapproval study. The Informed Consent Form (see Section 15.0) will detail the participant's obligations and rights under the study protocol. Attached to this form will be an Authorization to Disclose Health Information and Release Medical Records form, also to be signed by the participant (see Section 15.0). Both the Informed Consent Form and the Disclosure and Release Authorization address applicable privacy requirements.*

*The Informed Consent and Release Authorization Forms must be signed and presented to the surgeon before the participant can be enrolled into the postapproval study. The forms will be in triplicate. The surgeon will mail the original signed forms in a Business Reply Envelope (BRE), along with the sealed envelope containing the first (baseline) questionnaire, to the third party study entity. The surgeon will keep the second copy of the informed consent and medical records release authorization for retention in the participant's records. The third copy will be kept by the participant.*

*Consents and releases will be broad enough to secure permission to: access medical records required to be collected by this protocol; contact individuals that the participant has designated as a means to locate the participant; use Social Security Numbers to search proprietary databases (e.g., the National Change of Address (NCOA) database, the Social Security Death Index database, and other proprietary databases) as needed. Consents and releases will also permit participant data and information to be provided to the Food and Drug Administration (FDA), Institutional Review Boards (IRBs), and/or courts as needed. Additionally, informed consents and releases will make reference to the agreement of the participant to cooperate in allowing the third party study entity to obtain medical records required by this protocol.*

#### **14.0 RE-CONSENTING OF PARTICIPANTS DISCONTINUED DUE TO PATIENT NON-COMPLIANCE**

To maximize the collection of re-operation data, participants discontinued due to patient non-compliance prior to this protocol amendment will be offered the opportunity to re-consent and re-establish participation.

Prior to this protocol amendment, a participant was considered discontinued due to patient non-compliance when the following criteria were met:

- If, within the past three (3) years, the patient has not completed an annual follow-up questionnaire per the study protocol either on-line, by mail, or by telephone; and
- If, within the past three (3) years, a Surgeons Local Complication Form pertaining to an in-person office visit by the patient per the study protocol has not been filed by the investigating physician.

If a participant discontinued due to patient non-compliance presents for re-operation or secondary procedure they should be informed by the investigator that the protocol has been amended and there is an option to re-consent.

Participants discontinued due to patient non-compliance who wish to voluntarily reinstate participation will be provided with the IRB approved Addendum to Informed Consent for review. The investigating physician or designee will conduct the informed consent discussion. If the patient agrees to reinstate participation the Addendum to Informed Consent form will be signed and dated by both the participant and person obtaining consent.

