### 3.0 DESIGN

This protocol amendment includes participant follow-up only. Study enrollment has been closed since 15 Oct 2008 and no new study participants will be enrolled. Data collection will only take place if a participant requires a secondary procedure/reoperation. There are no longer requirements for scheduled office visits or annual participant questionnaires. The study is currently in year 7 and follow-up will continue through 10 years or until the National Breast Implant Registry opens for data collection, whichever occurs first.

As in the original protocol, there will be no concurrent controls needed as a source of comparison for secondary procedures/reoperations (see local complications category in original study design Tables 1 and 2). Thus, saline implant participants will not have data collected under this amended protocol.

Mentor will employ third party study entities that will be responsible for the following: (1) collecting data from surgeons; (2) entering data into and administering the study database; (3) generating follow-up reports as well as datasets; (4) meeting with Mentor on a regular basis; and (5) analyzing the study data. Mentor will be responsible for: (1) IRB approval; (2) monitoring third party entities; (3) analyzing the study data; and (4) periodic reporting to FDA.

The postapproval study was originally designed as follows:

*MemoryGel™ PAS uses a current cohort design of the first 41,900 women receiving Mentor's MemoryGel implants, with 10 years of follow-up. It will include augmentation, reconstruction, and revision patients, each in their naturally occurring proportions at participating study sites.*

*For the purpose of assessing rheumatological and neurological signs and symptoms, there also will be 1,000 saline breast implant patients from the participating surgeons' practices who will serve as concurrent controls. Concurrent control participants will be enrolled by approximately 30 physicians who routinely use saline implants. These investigative sites will be selected with the objective of obtaining the desired number of controls in an appropriate time frame, e.g. roughly the same time frame as the recruitment of MemoryGel subjects. These sites are to enroll all saline subjects meeting the specified eligibility criteria until 1,000 controls are recruited into this study.*

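### The only stated occasion for telling discontinued women about re-consent is a reoperation, which is the endpoint, and Section 11.1 gives no time origin, entry or risk-set rule for the Amendment 2 Kaplan-Meier estimate

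*Combined protocol and SAP*

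**What the plan says.** Section 14.0 states a general intention: "To maximize the collection of re-operation data, participants discontinued due to patient non-compliance prior to this protocol amendment will be offered the opportunity to re-consent". It gives no time, route or responsible person for that offer. The one occasion it names is this: "If a participant discontinued due to patient non-compliance presents for re-operation or secondary procedure they should be informed by the investigator" of the amendment and of the option to return. The section then provides for women who wish to come back voluntarily, without saying how they would learn that they can. For those who agree, the "Addendum to Informed Consent form will be signed and dated by both the participant and person obtaining consent".

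Section 13.0 adds that "A listing of participants and their status - active or discontinued (with reason for discontinuation) - will be provided to the investigative site" when Amendment 2 is initiated. It does not ask the site to contact the discontinued women.

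Under Section 3.0, "Data collection will only take place if a participant requires a secondary procedure/reoperation"; scheduled visits and annual questionnaires have ended.

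Section 2.0 makes Kaplan-Meier removal and reoperation rates an objective of the amended protocol. Section 11.1 (Complications/Reoperations) says that the cumulative incidence "will be estimated based on physician evaluations for the MemoryGel participants using Kaplan-Meier methodology", as time to first occurrence with 95% confidence intervals. The Amendment 2 report is described as "including data from the execution of Amendment 2 to the end of the study". Section 11.1 does not mention re-consented women. For the Amendment 2 estimate it states no time origin, entry date, risk set or censoring rule.

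**The concern.** A Kaplan-Meier estimate needs entry to the risk set to be independent of the event being counted. A woman who hears of re-consent because she has come for a reoperation, signs, and is then counted with that reoperation adds one event and almost no event-free time. A discontinued woman who has no reoperation meets no stated occasion on which she would be told. The numerator can therefore grow through a route that has no matching denominator.

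Removal is affected in the same way when the triggering procedure is an explantation, because the reoperation form in Section 16.0 records both. A returner may also have had an unrecorded reoperation while she was out of the study, so the triggering procedure need not be her first.

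The gap is wider than returners. Active women come under Amendment 2 observation at about year 7 (Section 3.0), and the plan does not say whether their time runs from implantation or from Amendment 2, or what happens to those already reoperated. These rates are the main product of the amended study, and two analysts could compute different ones from the same data.

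**Working it through.** **Plan's own figure.** There is none for the Amendment 2 estimate. Section 11.2 sizes only the original design (338,000 / 8.075 = 41,858 women, stated as 41,900), which has no bearing here.

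**Inputs.** From the documents: 41,451 MemoryGel women enrolled (Section 4.0) and at most about three years remaining, years 7 to 10 (Section 3.0). Assumed, because the documents give none of them:
- p = 9.3%, the true risk over the window, equal in active and discontinued women;
- D = 25% or 50% discontinued, and A = 1 - D active. This treats every non-active woman as eligible to re-consent, although Section 14.0 covers only non-compliance;
- u = 2% to 50%, the share of discontinued women's reoperations that enter through re-consent;
- c, the share of active women's reoperations that are reported; c = 1 unless stated.

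**Rule 1: returners pooled from the start of the window, with their triggering event counted.**
Estimate / true risk = (cA + uD) / (A + upD)

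**Rule 2: returners enter at re-consent, just before the event, and the event is counted (c = 1).**
Estimate / true risk = [1 - (1 - p)^((A + uD)/A)] / p

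| D | u | Rule 1 ratio | Rule 1 rate | Rule 2 ratio |
|---|---|---|---|---|
| 25% | 2% | 1.006 | 9.4% | 1.006 |
| 25% | 10% | 1.030 | 9.6% | 1.032 |
| 25% | 50% | 1.149 | 10.7% | 1.157 |
| 50% | 2% | 1.018 | 9.5% | 1.019 |
| 50% | 10% | 1.090 | 10.1% | 1.095 |
| 50% | 25% | 1.222 | 11.4% | 1.235 |
| 50% | 50% | 1.433 | 13.3% | 1.465 |

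In counts, at D = 50% and u = 25%: 20,726 active women with 1,927 events, plus 482 returners who all have events. (1,927 + 482) / (20,726 + 482) = 11.4%, against a true 9.3%.

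Rule 2 is no better than Rule 1, so delayed entry by itself does not help. The result depends little on p: at D = 50% and u = 2% to 50%, Rule 1 gives 1.02 to 1.46 for p = 5% and 1.02 to 1.40 for p = 15%.

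**Offset from missed events.** Under Rule 1 the ratio falls to 1 when c = 1 - u(1 - p)D/A.
- D = 25%: c = 0.994 at u = 2%, 0.970 at 10%, 0.849 at 50%.
- D = 50%: c = 0.982 at u = 2%, 0.909 at 10%, 0.546 at 50%.

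Below these values the estimate is too low even with returners' events included.

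**Effect of leaving those events out.** An active-only risk set has a ratio of about c, if discontinuation is unrelated to risk. At c = 1 it is unbiased. At c = 0.50 and D = 50% it gives 0.50, whereas Rule 1 gives 0.59 (u = 10%), 0.73 (u = 25%) or 0.96 (u = 50%). With poor capture, the cleaner rule can lie further from the truth.

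**The case against.** The strongest reply is that Section 14.0 promises re-consent without condition and allows voluntary return. A reader might infer that discontinued women without a reoperation are never brought back. The text does not say so: the reoperation visit is an instructed occasion, not an exclusive one, and the flow charts, the Addendum and Amendment 1 are not available here and could describe another route. What stands is that no other occasion is named, and that Amendment 2 leaves no scheduled event-free contact.

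Second, the size rests wholly on assumed inputs. Women enter this group after about three years without a completed questionnaire or a filed surgeon form ("If, within the past three (3) years, the patient has not completed an annual follow-up questionnaire per the study protocol" is the first criterion), so uptake may be low, and at 2% the ratio is close to 1. A reader might also take the 21.8% six-year follow-up rate as the active share; with assumed hazards of 1-5% per year and 5-50% uptake, that gives inflation of 1.15 to 2.65 times. The documents do not support this, because a follow-up rate is not a count of women still active.

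Third, a reader might fear that all discontinued women stay in the denominator to study end, which would make the rate too low. This is a weak reading: Section 13.0 separates active from discontinued women, and the Discontinuation Form carries a date.

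Fourth, removing returners' events can enlarge the net error when capture is poor. That is correct, and the fix has to say so. The estimate is also descriptive, with no comparator or test, which limits the consequences but does not supply the missing rule.

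**Conclusion.** The point holds and should be fixed; confidence is medium. The readable text ties the only named re-consent occasion to the endpoint, and Section 11.1 has no rule that stops such events from entering the estimate or that defines the risk set for anyone. If triggering reoperations are counted, this component biases the rate upward, by about 1.01 to 1.4 times under the assumptions above: p = 9.3%, equal risk in both groups, 25-50% discontinued, 2-50% uptake, full capture.

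A reader might infer that the reported rate will be too high overall. The documents do not support that. Amendment 2 has no scheduled visits or questionnaires and obtains no medical records (Section 10.0), so reoperations in active women may be missed, and the net direction is unknown.

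**What to change.** In Section 11.1, for the Amendment 2 report:

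1. Define the main risk set as MemoryGel women active when Amendment 2 is executed, identified from the Section 13.0 listing. Measure time from implantation, with delayed entry at that date. Exclude from the time-to-first analysis women whose first reoperation (or removal, for that endpoint) is already on record. The curve is then conditional on no recorded earlier event.
2. Admit a returner from her re-consent date only if no reoperation was planned at that time.
3. Leave reoperations that triggered re-consent out of the main estimate. Keep them in the reasons-for-reoperation table and report a sensitivity Kaplan-Meier estimate that includes them.
4. Add to the Amendment 2 form the re-consent date and a yes/no item on whether a reoperation was already planned at re-consent. The signed Addendum is dated, but none of the forms in Section 16.0 carries that date into the database.
5. Report the numbers discontinued for non-compliance, re-consented, and re-consented at an event.

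The cost is a short analysis rule and two form items. The main estimate will hold fewer events, and under-reporting in active women stays uncorrected. It should therefore be presented as a likely lower bound, assuming that discontinuation is unrelated to risk, beside the sensitivity estimate. The two need not bracket the truth: with low capture both can fall below it.
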